#### 5.7.13. Transfusion-impacted Period

The 14-day period following a transfusion of pRBCs or whole blood is defined as the transfusionimpacted period (ie, the interval between the transfusion day and the current study day is  $\leq$  13 days and includes the day of transfusion). An exception to this rule is that the transfusion-impacted period for haptoglobin is the 3-day period following a transfusion (ie, the interval between the transfusion day and the current study day is  $\leq$  2 days and includes the day of transfusion). Transfusion-impacted periods will only be taken into account for effectiveness endpoints.

The following parameters are impacted by pRBC or whole blood transfusion:

- Hemoglobin
- Reticulocytes
- PNH RBC (Type II and III red blood cells)
- Ratio of PNH RBC to PNH WBC
- FACIT-Fatigue
- Haptoglobin (transfusion-impacted period is limited to 3 days instead of 14)

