#### **3.2.3.** Pharmacodynamic (PD) Endpoint

• PD and complement biomarker measurements will include PNH RBC and white blood cell (WBC) clone size, plasma Factor Bb and AP activity (as assessed via AP Hemolysis and AP Wieslab).

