#### CONFIDENTIAL

impacted period, the average of all (central and local labs) pre-treatment values from the Screening visit up to Day 1 pre-dose will be used to determine a baseline value, even if these values are themselves impacted by transfusion. This will lead to a conservative estimate of the baseline as the values could be impacted by transfusion and may be higher than expected as a result.

Derivation of the baseline for the following parameters: reticulocytes, PNH RBC (Type II and III red blood cells), the ratio of PNH RBC to PNH WBC (Type II and III granulocytes), haptoglobin, and FACIT-Fatigue will be as stated for Hb, above.

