## 11.2. Pharmacodynamic Analyses

In this study, PD assessments include PNH clone size (RBC and WBC), Factor Bb, serum AP activity as assessed by AP Wieslab, and additional exploratory assays.

Descriptive summaries of the above assessments including change from baseline will be presented by treatment category, dose regimen, and study visit. AP Wieslab (and other similar assays, if applicable) will be reported only as percent of baseline, not as actual value or percent change from baseline. Data values will be listed.

If PD assessments are reported with inequalities ( $<, \leq, >, \text{ or } \ge$ ), the same conventions used for laboratory values as described in Section 9.2 will be used.

Any further analysis of PD data including the relationship to PK concentrations will be performed under a separate analysis plan.

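### The SAP does not settle whether its transfusion rule covers PNH RBC clone size in the PD table, so donor-diluted visit values may be compared with a screened baseline

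*SAP*

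**What the plan says.** **The rule and its scope.** SAP 5.7.13 begins: "The 14-day period following a transfusion of pRBCs or whole blood is defined as" the transfusion-impacted period (3 days for haptoglobin). It lists the affected parameters, among them PNH RBC (Type II and III) and the ratio of PNH RBC to PNH WBC. It also says: "Transfusion-impacted periods will only be taken into account for effectiveness endpoints".

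**Where clone size belongs.** SAP 3.2.3 makes it a PD endpoint: "PD and complement biomarker measurements will include PNH RBC and white blood cell (WBC) clone size". It is absent from the effectiveness list in SAP 8 and from the clinical measurements in SAP 10.1.2. SAP 11.2 says of the PD assessments: "Descriptive summaries of the above assessments including change from baseline will be presented by treatment category, dose regimen, and study visit". That section states no transfusion rule. The output is Table 14.5.1 (PD population).

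**Baseline.** SAP 5.6 excludes hemoglobin values taken within 14 days after a transfusion and applies the same derivation to other parameters, in a sentence that starts: "Derivation of the baseline for the following parameters: reticulocytes, PNH RBC (Type II and III red blood cells". Its list also covers the RBC/WBC ratio. If no unaffected value exists, all pre-treatment values are averaged, "even if these values are themselves impacted by transfusion".

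**Text pointing the other way.** SAP 5.7.13.1 and 5.7.13.2 each close by applying the hemoglobin value-selection algorithm to all other listed parameters. SAP 9.2, on safety laboratory data, says hemoglobin and the other affected parameters follow the 5.7.13 rules. Safety Table 14.3.3.2 includes PNH clone size.

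**The concern.** Donor red cells are not PNH cells, so a transfusion lowers the measured PNH RBC fraction with no change in disease. Protocol 13.7 describes the drug as reducing hemolysis of PNH red cells, so better control should preserve or raise this fraction. Dilution pushes the reading the opposite way.

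If visit values are left unscreened while the baseline is screened, the mean change from baseline is pulled down by recently transfused subjects. Table 14.5.1 is split by treatment category and dose regimen, so one such subject can matter in a small cell. Two programmers could also follow the SAP in good faith and produce different clone-size summaries for the same subjects and visits in Tables 14.3.3.2 and 14.5.1. Characterizing drug effect by PD biomarkers is a stated secondary objective (SAP 3.1.2).

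**Working it through.** The plan gives no figure to reproduce. The check is a comparison of the text, followed by an illustration of size.

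**1. What each section implies for post-baseline PNH RBC clone size**

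| SAP section | Implication |
|---|---|
| 5.7.13, scope sentence | Not screened: not an effectiveness endpoint |
| 5.7.13.1 (South Africa) | Opens as an algorithm for effectiveness analysis; closes by extending it to all listed parameters |
| 5.7.13.2 (other countries) | Screened: extended to all listed parameters |
| 9.2, Table 14.3.3.2 (safety) | Screened, although not effectiveness |
| 11.2, Table 14.5.1 (PD) | Silent |

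SAP 9.2 cannot simply be carried over to Table 14.5.1, because it opens by describing non-PK/PD samples.

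**2. Three possible readings**

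- *Scope sentence literal, 5.6 as written:* baseline screened where possible, visit values in Table 14.5.1 not. The comparison is asymmetric. If 9.2 is followed for Table 14.3.3.2, the two tables also differ.
- *5.7.13.1, 5.7.13.2 and 9.2 govern everywhere:* both sides screened, no asymmetry.
- *Scope sentence also limits 5.6:* neither side screened. The asymmetry goes, but diluted values remain and the 5.6 sentence naming PNH RBC has no use.

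The SAP does not choose among them.

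**3. Size under the first reading.** The inputs c, d and f are assumptions; the documents give none of them.

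Let c be the true clone and d the donor share of circulating red cells. Observed clone = c × (1 − d), so bias = −c × d.

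| True clone c | d = 10% | d = 20% | d = 30% |
|---|---|---|---|
| 40% | −4 points | −8 | −12 |
| 60% | −6 | −12 | −18 |
| 80% | −8 | −16 | −24 |

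The sign can reverse. With a baseline of 60%, a true rise to 70% and d = 20%, the visit reads 0.70 × 0.80 = 56%, a change of −4 instead of +10 points.

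The RBC/WBC ratio r would read r × (1 − d), a relative fall of 10% to 30%, if the WBC clone is unaffected. The SAP does not list the WBC clone as affected.

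If a fraction f of subjects at a visit are inside the window, the visit mean shifts by f × bias. For c = 80%, the shift runs from 0.05 × (−8) = −0.4 points to 0.30 × (−24) = −7.2 points.

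**4. How often a visit falls in the window.** The window is 14 days including the day of transfusion. Visits are 28 days apart to Week 96 and 56 days apart afterwards (SAP 3.7). For one transfusion at a random time between visits, the chance that the next visit is inside the window is 14/28 = 50%, or 14/56 = 25%. If transfusions are mostly prompted by the hemoglobin at a visit, they fall early in the interval and the chance is lower.

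**The case against.** The strongest reply is that the SAP already screens clone size. Two sections extend the algorithm to every listed parameter, 9.2 applies it outside effectiveness, and listing PNH RBC in 5.7.13 would serve little purpose otherwise. This stands in part. A reader might infer that Table 14.5.1 will certainly compare diluted values with a clean baseline, and the documents do not support that certainty. Nor do these sections settle the matter: they contradict an explicit scope sentence, and 11.2 does not refer to them.

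A second reply is that the scope sentence may also limit the baseline rule, which would remove the asymmetry. This is possible, but 5.6 sets its own 14-day exclusion for these parameters without limiting it to effectiveness.

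Third, the baseline is not always clean. This stands. The fallback admits affected values, and direct rollovers have no screening visit, so they may have few alternatives.

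Fourth, Protocol 12 places PD sampling under its efficacy heading, so clone size might count as effectiveness. The SAP does not treat it so: it is outside SAP 8 and 10.1.2 and is analyzed in the PD population.

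Finally, it is tempting to say that the ratio has no planned summary. That cannot be pressed. The exploratory endpoints are not visible, 11.2 allows further exploratory assays, and display specifications are in a separate document.

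**Conclusion.** The SAP contradicts itself on whether post-baseline PNH RBC clone size is screened for transfusion, and the PD section is silent. Followed literally, the scope sentence sets donor-diluted visit values in Table 14.5.1 against a baseline screened whenever an unaffected value exists. The same variable may then be handled differently in Table 14.3.3.2.

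The illustrated bias is 4 to 24 points downward per affected subject, for assumed donor shares of 10% to 30% and true clones of 40% to 80%. The effect on a visit mean depends on the fraction recently transfused, which the documents do not give. A reader might also infer a distorted comparison between the C5-inhibitor-naïve and inadequate-response categories. That would need different transfusion rates, and the documents report none.

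The affected output is a descriptive PD summary in an uncontrolled study, and the primary safety endpoint is not at stake. This is a minor to moderate correction.

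**What to change.** - Amend the scope sentence in SAP 5.7.13 so that the rule also covers PNH RBC clone size, and the RBC/WBC ratio wherever it is summarized, in the PD and safety laboratory tables.
- Add a cross-reference in SAP 11.2 to the algorithm in 5.7.13.1 and 5.7.13.2: use an unaffected pre-transfusion value, otherwise set the visit to missing.
- Apply it identically in Tables 14.5.1 and 14.3.3.2, and keep all measured values in the listings (16.2.19 for PD, 16.2.13.2 for hematology).

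Dropping the baseline screening for these two parameters would also make the comparison symmetric, but it would leave diluted values on both sides.

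The cost is a few sentences and reuse of an algorithm already specified. The downside is fewer, or carried-back, values at visits that follow a transfusion; a footnote counting substituted and missing values per visit would make this visible.

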## 5.7.13.1. Transfusion-impacted Period for South Africa

The algorithm as defined below aims to exclude transfusion impacted lab measurements when possible, and acts to select local lab measurements over central lab measurements (for South Africa subjects) or central lab measurements over local lab measurements (for subjects outside of South Africa), when possible. This is due to a lack of reliable data obtained from the central lab in South Africa.

For South African sites, the algorithm for determining which values should be used in effectiveness analysis are as follows:

The Hb value to use for a particular visit is provided below. The first item matching the description in the list should be used.

- 1. Local lab value for Hb at the visit of interest closest to the target day.
  - a. If multiple results are equidistant from the target, use the latest.
  - b. If multiple records exist on the same day, find the median of the results on that day (for grading, set to the most frequent grade or worst grade if two grade have the same frequency).
- 2. Central lab value for Hb at the visit of interest closest to the target day.
  - a. If multiple results are equidistant from the target, use the latest.
  - b. If multiple records exist on the same day, find the median of the results on that day (for grading, set to the most frequent grade or worst grade if two grade have the same frequency).

If the value at the visit of interest was taken during a transfusion-impacted period:

- 3. Local lab pre-transfusion value that itself was not within 14 days after the subject received a pRBC or whole blood transfusion.
  - a. If multiple results are equidistant from the target, use the latest.
  - b. If multiple records exist on the same day, find the median of the results on that day (for grading, set to the most frequent grade or worst grade if two grade have the same frequency).
- 4. Central lab pre-transfusion value that itself was not within 14 days after the subject received a pRBC or whole blood transfusion.
  - a. If multiple results are equidistant from the target, use the latest.
  - b. If multiple records exist on the same day, find the median of the results on that day (for grading, set to the most frequent grade or worst grade if two grade have the same frequency).

If no value meets the criteria listed, the Hb at the visit of interest will be set to missing and will not be summarized. This same algorithm will be used for all other transfusion-impacted parameters (Section 5.7.13), however haptoglobin will use a period of 3 days after transfusion instead of 14 days.

## 5.7.13.2. Transfusion-impacted Period for Other Countries

The Hb value to use for a particular visit is provided below. The first item matching the description in the list should be used.

- 5. Central lab value for Hb at the visit of interest closest to the target day.
  - a. If multiple results are equidistant from the target, use the latest.
  - b. If multiple records exist on the same day, find the median of the results on that day (for grading, set to the most frequent grade or worst grade if two grade have the same frequency).
- 6. Local lab value for Hb at the visit of interest closest to the target day.
  - a. If multiple results are equidistant from the target, use the latest.
  - b. If multiple records exist on the same day, find the median of the results on that day (for grading, set to the most frequent grade or worst grade if two grade have the same frequency).

If the value at the visit of interest was taken during the transfusion-impacted period:

- 1. Central lab pre-transfusion value that itself was not within 14 days after the subject received a pRBC or whole blood transfusion closest to the target day.
  - a. If multiple results are equidistant from the target, use the latest.
  - b. If multiple records exist on the same day, find the median of the results on that day (for grading, set to the most frequent grade or worst grade if two grade have the same frequency).
- 2. Local lab pre-transfusion value that itself was not within 14 days after the subject received a pRBC or whole blood transfusion
  - a. If multiple results are equidistant from the target, use the latest.
  - b. If multiple records exist on the same day, find the median of the results on that day (for grading, set to the most frequent grade or worst grade if two grade have the same frequency).

If no value meets the criteria listed, the Hb at the visit of interest will be set to missing and will not be summarized. This same algorithm will be used for all other transfusion-impacted parameters, however haptoglobin will use a period of 3 days after transfusion instead of 14 days.

#### CONFIDENTIAL

For FACIT-Fatigue, since the scale is not captured at unscheduled visits, any FACIT-Fatigue occurring within a transfusion-impacted period will not be summarized on the tables but will be presented in the listings.

## 5.8. Multicenter Studies

No adjustment for multiple centers is planned.

## 5.9. Stratification

No stratification is planned.

## 5.10. Examination of Subgroups

No subgroups are planned.

## 5.11. Multiple Comparisons and Multiplicity

No adjustment for multiple comparisons is planned.

## 5.12. Data Handling Conventions

#### 5.12.1. Premature Withdrawal and Missing Data

No missing data will be imputed, except dates and times as mentioned above.

## 5.12.2. Dropouts

Subjects will not be replaced if they discontinue study drug.

## 5.13. Values of Clinical Concern

Values of clinical concern include events of special monitoring (EOSMs), which are AEs or safety topics for which special monitoring, additional data collection activities, and/or enhanced signal detection activities within BioCryst are considered appropriate for this population and study. EOSMs for this study include hemolysis, SARS-CoV-2 infections (asymptomatic and symptomatic),

## 5.14. Events of Special Interest

For this study, severe infections will be considered events of special interest (EOSIs).

## 6. TREATMENT COMPARISONS

## 6.1. Data Display Treatment and Other Sub-Group Descriptors

Planned treatment categories to be displayed on the summary tables are defined by whether the subject was naïve to both eculizumab and ravulizumab (C5 inhibitor [C5-INH] naïve) or had an inadequate response to either eculizumab or ravulizumab (C5-INH inadequate response). Subjects who have not taken either eculizumab or ravulizumab within the previous calendar year are considered naïve. Subjects whose parent study is BCX9930-202 are considered inadequate response subjects, and subjects whose parent study is BCX9930-203 are considered naïve subjects. These categories may be changed; if so, the final treatment categories will be used in the data displays.

## Table 4:Planned Treatment Categories

C5-INH Naïve	
C5-INH Inadequate Response	

## 6.2. Significance Tests

If performed, unless otherwise specified, by-treatment significance tests will use a two-sided 0.05 significance level for p-values and confidence intervals (CIs).

## 7. STUDY POPULATION

## 7.1. Disposition of Subjects

Subject disposition will be presented for all subjects. The number and percentage of subjects who completed the study and discontinued from the study will be provided. The reasons for early discontinuation at any point also will be presented by planned treatment category. These data will also be listed by treatment and subject. Duration on study treatment during Study 201 and from the beginning of the previous study will also be provided.

The number and percentage of subjects included in the Safety, PK, and PD populations will be presented by treatment category.

## 7.2. Protocol Deviations

Protocol deviations will be identified and displayed in data listings by treatment, subject, and (where applicable) date of deviation. Deviation category, major or minor status, and importance will be listed if included in the received deviation data.

## 7.3. Demographic and Baseline Characteristics

Demographic data and baseline characteristics including age, race, ethnicity, sex, height (if available), weight, and body mass index (BMI) (if available) will be summarized using descriptive statistics for the Safety population, presented by treatment category. If not collected, baseline BMI will be calculated as  $BMI = weight (kg)/[height (m)^2]$  to one decimal place. Time from last BCX9930 dose to baseline will be summarized and listed as applicable.

## 7.4. Medical History

Medical history will be coded using the Medical Dictionary for Regulatory Affairs (MedDRA) version 24.0 and listed.

## 7.5. Prior and Concomitant Medications

Medications will be classified as prior or concomitant and coded using the World Health Organization (WHO) drug dictionary version B3 March 2021. Concomitant medications will be summarized, and prior medications may be summarized, by descending frequency of Class 4 term, preferred term (PT), and treatment. Medications will be listed by treatment category and subject.

## 7.6. Exposure and Compliance

Subjects will receive kits containing BCX9930 per the schedule of assessments for self-administration at home. The number and percentage of subjects exposed to BCX9930, and the number of days of exposure to BCX9930 in Study 201 and including the parent study will be summarized by treatment category. Individual kit data will be listed by treatment, subject, and date issued.

#### CONFIDENTIAL

Compliance will be determined from the Study 201 Study Drug Accountability form kit data as tablets dispensed minus tablets returned, multiplied by 100, divided by the total number of tablets of study drug which should have been taken according to the Protocol and dose escalation and reduction records. Compliance data will be summarized by treatment and listed by treatment and subject.

## 8. EFFECTIVENESS

The following effectiveness endpoints will be summarized and listed:

- Durability of response
- Hematological response (categorization of response according to criteria in Table 5)
- PROs: QLQ-AA/PNH, FACIT fatigue scale, TSQM scores
- Clinical measurements of PNH (LDH, hemoglobin, haptoglobin, reticulocytes, transfusions)
- Subjects with dose escalation
- Discontinuations due to lack of efficacy
- Disease severity as recorded by the PNH symptoms assessment

#### 8.1.1. Durability of Response

Durability of response will be summarized using absolute and change from baseline in hemoglobin measures throughout the study. Plots of mean change from baseline hemoglobin by treatment category and time point will be produced.

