9.1. Concomitant Medications

During the course of the study, the investigator should review the subject's medication list for potentially nephrotoxic medications and consider, when medically feasible, whether these medications may be stopped or substituted with non- or less nephrotoxic medications. Caution should be exercised with the chronic use of non-steroidal anti-inflammatory drugs (NSAIDs) while taking BCX9930. Subjects may take their normal medications, with the exception of any changes to nephrotoxic medications and prohibited medications detailed below (Section 9.2).

Vaccination against *N. meningitidis* types A, C, W, Y, and B, *S. pneumoniae*, *H. influenzae* type B (Hib) and varicella zoster virus (VZV) will be allowed up to at least 14 days prior to Day 1.

As part of their treatment for PNH, subjects should be assessed by the investigator for infection risk as described in Section 11.3.2. Prophylactic antibiotic and/or antiviral medications may be considered if clinically indicated (eg, valacyclovir/acyclovir if subject is seropositive for VZV or tenofovir/lamivudine if at risk for reactivation of HBV).

Subjects may be encouraged to begin tapering or to discontinue medications that suppress the immune system if clinically indicated.

Based upon the mechanism of action of proximal AP inhibition targeting Factor D and demonstration that BCX9930 monotherapy is sufficient to control hemolysis in PNH in C5 inhibitor-naïve subjects (see Section 5.4), subjects who commence the study with a background treatment of eculizumab or ravulizumab should be considered for a discontinuation of these medications. The treating Investigator should discontinue the C5 inhibitor once the subject is on an optimized dose of BCX9930. It is expected that all subjects will discontinue background C5 inhibitor therapy as there should be no pharmacological benefit to terminal AP inhibition with effective proximal AP inhibition via BCX9930, unless there is a medical reason not to do so. In this case, discontinuation from the study should be considered if the medical reason is nonresponse to BCX9930 therapy.

Details of all prior (within 30 days of Screening) and concomitant medication use, including all medications administered for the treatment of AEs, will be recorded in the source documentation/case report form (eCRF).

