11. STUDY CONDUCT

11.1. Overview

This is an open-label, non-randomized study to evaluate the long-term safety and effectiveness of daily oral BCX9930.

Subjects will be eligible to receive study drug (BCX9930) for up to 144 weeks, until drug is available by another mechanism (eg, expanded or market access) or until the Sponsor discontinues development of the product for PNH (See Section 7.4), whichever comes first. Study drug will be discontinued for subjects who are deriving no clinical benefit, are intolerant of study drug, or experience an unacceptable drug-related TEAE as defined in more detail in Section 7.4. The Study will be discontinued if ongoing regulatory or Institutional Review Board/Ethics Committee (IRB/EC) approval is withdrawn, or in the event that technical or logistical factors prevent the ongoing conduct of the study. Subjects who discontinue study drug will have a minimum of 3 days hemolysis testing and then return to the clinic for an end-of-study visit 3 weeks after the last dose of study drug.

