14.3.3. Missing Data

For subjects who prematurely discontinue the study, all available data will be included for the key safety and effectiveness analyses.

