## 5.4. Data Presentation Conventions

Continuous data will be summarized using the number of subjects with available data, mean, standard deviation (SD), standard error of the mean (SE), median, and minimum and maximum. Categorical data will be summarized using counts and percentages. Percentages are calculated using the total number of subjects per treatment group unless otherwise specified.

Unless otherwise specified, means and medians are formatted to one more decimal place than the measured value, SDs, SEs, confidence interval (CI) limits, and coefficient of variation (CV) to two more decimal places, and minimum and maximum values to the same number of decimal places. For categorical variables, the number and percentage of responses will be presented in the form XX (XX.X%) where the percentage is in the parentheses, except that 100% will be presented to three digits with no decimal. Dates will be formatted DDMMMYYYY and times will be formatted in 24-hour time as HH:MM. Partial dates will be handled as described in Sections 5.7.10 and 5.7.11. P-values and CIs will use a two-sided 0.05 significance level unless otherwise noted; p-values will be presented with three decimal places. Extreme p-values or CIs will be presented as "<0.001" and ">0.999" with the appropriate number of places.

All BCX9930 concentrations will be reported as provided by the concentration vendor.

Wherever possible, data will be decimal aligned.

CONFIDENTIAL

A table of contents at the end of this SAP provides the expected titles and numbers of the tables, listings, and figures of the final report. Changes to titles or numbering in the final report will not necessitate a revision to the SAP, nor will it be considered a deviation from planned analyses. Additional data listings supporting the tables will not be considered a deviation from planned analyses.

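### Durability of response (SAP 8.1.1) is observed-case hemoglobin by visit, so the mean can stay flat while responses are lost, and no individual response is followed

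*SAP*

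**What the plan says.** - **Endpoint.** Durability of response heads the effectiveness list in Protocol 14.3.7, which leaves the details to the SAP, and in SAP 8. SAP 8.1.1 then says: "Durability of response will be summarized using absolute and change from baseline in hemoglobin measures throughout the study". It adds: "Plots of mean change from baseline hemoglobin by treatment category and time point will be produced". Neither document defines a responder, a loss of response or a duration for this endpoint.
- **Who is counted.** SAP 5.4: "Continuous data will be summarized using the number of subjects with available data, mean" and the usual other statistics. SAP 5.12.1: "No missing data will be imputed, except dates and times as mentioned above". Protocol 14.3.3: "For subjects who prematurely discontinue the study, all available data will be included for the key safety and effectiveness analyses".
- **Who leaves.** Protocol 11.1: "Study drug will be discontinued for subjects who are deriving no clinical benefit". For subjects kept on a C5 inhibitor for a medical reason, Protocol 9.1 says that "discontinuation from the study should be considered if the medical reason is nonresponse to BCX9930 therapy".
- **Follow-up after stopping.** At least 3 days of hemolysis monitoring and one end-of-study visit 3 weeks after the last dose (Protocol 11.3.5 and 11.3.7).
- **Related displays.** SAP 8.1.2 tabulates hematological response by count and percentage at Weeks 24, 48, 72, 96, 120 and 144. SAP 8.1.4.3 states that the eCRF did not record lack of efficacy as a reason for discontinuation.

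**The concern.** Durability is a question about individuals: of those who had a response, how many still have it, and for how long? A visit mean over whoever is still present answers a different question. In this study presence is tied to the outcome, because lack of benefit is a ground for stopping drug and follow-up ends soon afterwards. Later means are therefore weighted towards subjects who are doing well.

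Continued effectiveness during long-term treatment is a stated secondary objective, and the display labelled durability is where a reader will look for it. A level curve there would naturally be read as lasting response.

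**Working it through.** The plan has no figure to reproduce: there is no sample size calculation, loss rate or dropout rate. The rates and falls below are assumptions, varied over a range.

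**Step 1: one visit.** Let L be the share of subjects who have lost response, d their fall in hemoglobin (g/dL), and w the share of those losers with no value at the visit. Subjects who keep response have change 0.

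- All-subject mean change = -L·d
- Observed mean change = -L(1-w)d / (1-L·w)

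For L = 0.30 and d = 3, the all-subject value is -0.30×3 = -0.90. The observed values are:

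- w = 0.5: -(0.30×0.5×3)/(1-0.15) = -0.45/0.85 = -0.53
- w = 0.8: -(0.30×0.2×3)/(1-0.24) = -0.18/0.76 = -0.24
- w = 1.0: 0.00

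| L | d | All subjects | Observed, w=50% | w=80% | w=100% |
|---|---|---|---|---|---|
| 10% | 2 | -0.20 | -0.11 | -0.04 | 0.00 |
| 30% | 3 | -0.90 | -0.53 | -0.24 | 0.00 |
| 40% | 3 | -1.20 | -0.75 | -0.35 | 0.00 |

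A shift common to all subjects adds equally to both means and leaves the gap unchanged. A simulation of the middle row at w = 80% (200 subjects, 4,000 runs, assumed SD of change 1 g/dL) gives -0.23 observed against -0.90 for all subjects, with about 152 of 200 observed.

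**Step 2: over time, with every low value recorded once.** Suppose a share q of remaining responders loses response in each 24-week period, falls by 3 g/dL, contributes one low value and then leaves. At period k:

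- Share observed = (1-q)^(k-1)
- Observed mean change = -3q, the same at every period
- All-subject mean change = -3[1-(1-q)^k]
- Share still responding = (1-q)^k

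For q = 0.10:

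| Week | Observed mean | All-subject mean | Still responding | Share observed |
|---|---|---|---|---|
| 24 | -0.30 | -0.30 | 90% | 100% |
| 48 | -0.30 | -0.57 | 81% | 90% |
| 72 | -0.30 | -0.81 | 73% | 81% |
| 96 | -0.30 | -1.03 | 66% | 73% |
| 120 | -0.30 | -1.23 | 59% | 66% |
| 144 | -0.30 | -1.41 | 53% | 59% |

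For q = 0.05 the observed mean is flat at -0.15. By Week 144 the all-subject mean is -0.79 and 73.5% still respond.

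**Step 3: what the 6-month response table would show.** With L = 30%, the share in response is 70% on a full denominator, whatever w is. On an observed-only denominator it is (1-L)/(1-L·w), which gives 82%, 92% or 100% for w = 50%, 80% or 100%. SAP 5.4 makes the full treatment group the default denominator, so the table would show the loss if the default is used.

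**The case against.** The best defence is that the plan has several safeguards outside 8.1.1.

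- **Response table.** Response categories are reported every 6 months, by default on all subjects in the group. Step 3 shows that this exposes net loss.
- **Table n and disposition.** The number with data is a required table statistic. Disposition and discontinuation reasons are tabulated, and Protocol 14.3.4 promises counts completing through each visit.
- **Recorded low values.** Visits are 4-weekly to Week 96, and SAP 5.7.12 assigns unscheduled and early-termination visits to analysis windows. Many falls would be recorded before the subject leaves.
- **Status of the endpoint.** This is an uncontrolled safety study, and durability is not in the list of secondary endpoints.

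Much of this stands. A reader might infer that the plan cannot show lost response at all, but SAP 8.1.2 rules that out. A reader might also infer that the mean would not move. That is only the w = 100% case: with everyone starting at 12 g/dL and 25% falling unseen to 9, the observed mean stays at 12.0 while the all-subject mean is 0.75×12 + 0.25×9 = 11.25. The documents do not support taking that extreme as the expected result.

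The exit rule is also softer than Protocol 11.1 alone suggests. It refers to Section 7.4 for detail, and 7.4.1 does not name lack of benefit; it leaves room for investigator judgment.

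The defence does not remove the point. The response table is cross-sectional, so it cannot tell the same responders persisting from losses offset by new responders. On the full denominator it also mixes lost responses with subjects stopped administratively or not yet at the visit. Its denominator could still be set otherwise, because display specifications sit in a separate document. The plots have no stated requirement to show n. Windowing a last low value does not cure the bias: Step 2 allows for one and the curve is still flat.

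**Conclusion.** The point holds at moderate strength. The analysis named durability of response does not follow any response, and its observed-case mean can look stable while responses are lost. How far it would mislead depends on how many subjects lose response and leave, which the documents do not give. Over the assumed range in Step 1, the gap between the all-subject and observed means runs from about 0.1 g/dL (10% losing 2 g/dL, half unobserved) to 1.2 g/dL (40% losing 3 g/dL, all unobserved). These figures are illustrations, not forecasts, and they assume that subjects who keep response do not change.

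The primary safety objective is unaffected. This is a low-cost improvement to one secondary objective, not a flaw that undermines the study.

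**What to change.** 1. Keep the hemoglobin summaries in SAP 8.1.1 and print n under each time point of the mean-change plot.
2. Add a subject-level durability table. At each 6-month point, give the share of all mITT subjects due for that visit who are in good response or better. Count non-administrative stops as not in response. Exclude subjects who have not yet reached the visit or who stopped administratively. In SAP Table 5 this cut requires no RBC transfusion and a median hemoglobin of at least 10 g/dL.
3. Support it with Kaplan-Meier time to the first 6-month period below good response, among all subjects who reach good response or better. Count a non-administrative stop as loss and censor administrative stops. Do not restrict the durability analysis to Week 24 responders, which would omit earlier losses; the table in item 2 covers those.
4. Because the eCRF lacks a lack-of-efficacy reason, treat all non-administrative stops as loss in the main version. Add a sensitivity analysis that censors stops recorded as due to an AE.
5. Reconcile Protocol 11.1 with 7.4.1 on lack of benefit, so that the grounds for stopping are stated consistently.

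The cost is one or two extra displays, built from categories already derived and a method that SAP 9.1 already uses for other events. Stops must also be sorted into administrative and other. Durability may look less favourable, the composite mixes tolerability stops with loss of efficacy, and the good-response cut leaves out subjects who benefit at partial response. The cut and the stop rules should therefore be fixed before the analysis.
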